This study is important because it targets the health and well-being of the mother-infant-male partner triad,^[50] the essential family group that has eluded effective engagement strategies in HIV care. It builds on our research team's extensive experience in: (1) HIV care and treatment; (2) male partner engagement; (3) and cost-effectiveness analysis. Our results will improve outcomes by effectively engaging couples in HIV care and treatment during pregnancy and beyond. Without effective innovation in culturally appropriate adherence support to all stages of the care continuum, EMTCT efforts will fail in rural Africa.

6. Design and Study Questions

We propose to conduct a matched-pair cluster Randomized Controlled Trial to evaluate the effects of our intervention. To our knowledge, this is the first ANC-based couples study that will assess definitive treatment outcomes within a randomized controlled trial (RCT), and analyze the cost-effectiveness of the intervention. Twenty-four primary and secondary level health care facilities in Zambézia Province will be matched and then randomized to the control (standard-of-care [SOC]) or intervention (HoPS+) arms (12 sites per arm). We opted for a study design in which the unit of randomization is the EMTCT clinic (not the individual) because it would be extremely difficult to implement the intervention to only a subset of clients within each facility. We will match clinics on ART uptake rates, retention in care among patients on treatment, patient volume, HIV prevalence in ANC, and level of facility (secondary or primary)^[51] using reweighted Mahalanobis distances^[52] and then randomize clinics in each matched pair to intervention and SOC arms – 12 clinics per arm, 24 total. Intervention and control sites will be >100 km of each other to prevent contamination.

There are four specific study questions:

Question 1: Is our intervention idea (partners-based ART services for expectant and post-partum couples) acceptable to expectant couples?

Question 2: Does our intervention positively impact partner support for ART medication adherence and retention in care? Does it increase empathy among partners enrolled? Does it increase knowledge about HIV? Does it reduce HIV stigma among couples enrolled into the intervention?

Question 3: Does our intervention improve the proportion of exposed infants who are tested for HIV (early infant diagnosis)? Does it decrease the number of infants who are HIV-positive at 12 months?

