Question 4: Is the intervention cost-effective? Would the Ministry of Health be willing to scale it up based on our costing data?

7. Study Population

a. Population:

Couples consisting of two adults 18 years or older (one HIV-infected pregnant woman and her HIV-infected male partner) presenting for ANC services together at one of 24 clinical sites in Zambézia province.

b. Inclusion Criteria:

Couples, one HIV+ pregnant woman and her infected male partner, will be eligible to participate if the woman's due date is >2 weeks from enrollment. Both persons must also be 18 years or older, able to give consent, willing to consent to an infant record search, and must agree to enroll in ART together.

c. Exclusion Criteria:

Couples will not be eligible to participate in the study if the woman is not pregnant, if both persons are not HIV+, if either person is younger than 18 years, if one member of the couple is unwilling to enroll in ART or consent to the infant record search, or if one member of the couple is unable to give consent due to mental limitations.

d. Calculations of Sample Size:

Objectives 1 & 3: With 24 clusters and 45 couples per cluster, we have over 80% power to detect a 30% increase in the proportion of pregnant women who initiate ART from 55% to 71.5% with $\alpha = 0.05$. Our power calculations count adults and babies who dropout during the EMTCT cascade (e.g. do not initiate ART) as failures for downstream aims (e.g. retention on ART or viral suppression). For example, SOC ART retention was calculated as the proportion of women who initiated ART multiplied by the proportion of women retained in care ($0.55 \times 0.56 = 0.31$). In our sample size calculation, we power for a 20% increase in adult ART retention (above and beyond the 30% increase in adult ART initiation, for an improvement in retention from 31% to 48%), 90% vs. 80% viral suppression among women or men, 20% increase in EID testing, and 40% reduction in infant HIV positivity. Women, men and infants will be evaluated as separate study populations.

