Friends in Global Health supports HIV care and treatment services to 88 clinical sites in the province. Our trial will involve 24 of these clinics. These sites range from small district-level hospitals to rural health posts. All provide Option B+ services free of charge to HIV-infected pregnant women and their partners. In 2015, FGH clinics tested 95% (114,857) of the pregnant women presenting for ANC for HIV and provided Option B+ ART services to 87% (8,137 newly diagnosed women); 3,000 HIV-infected men were identified through ANC-based couples counseling.

Table 2: Study Sites by intervention Status

	Intervention sites		Control sites	
	Health Facility	District	Health Facility	District
1	Muiane CS III	Gilé	Mocubela CS III	Mocubela
2	Mixixine CS III	Namacurra	Inhassunge CS I	Inhassunge
3	Palane-Mucula CS II	Inhassunge	Mugubia CS	Namacurra
4	Gurai PSA	Mocubela	Bingagira PS	Inhassunge
5	Muebele PS	Namacurra	Gonhane CS III	Inhassunge
6	Maganja da Costa CS III	Maganja dC	Gilé CS II	Gilé
7	Naburi CS III	Pebane	Tapata CS III	Mocubela
8	Nante CS III	Maganja dC	Malei PS	Namacurra
9	Tomeia PSA	Pebane	Pebane CS II	Pebane
10	7 de Abril CS III	Pebane	Magiga PSA	Pebane
11	Pele-Pele CS	Pebane	Alto Maganha CS	Pebane
12	Madal CS	Quelimane	M'Baua CS III	Namacurra

10. Data Management and Analysis

Data Management and Security

The data collected will be kept in a database housed in Mozambique. Data will be stored in a restricted access folder that sits on the FGH server. In addition, data will be password-protected to limit access to staff involved in the study and to ensure confidentiality. Data will be encrypted, backed up on FGH servers, and uploaded to the Vanderbilt servers as needed for PI access. FGH servers have daily backups scheduled; therefore, all data will be backed up on a day-to-day basis.

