For this project, de-identified data will be extracted into a restricted dataset by FGH employees from the existing OpenMRS databases and sent to a VUMC Biostatistician for analysis. All routine programmatic data are owned by the MOH. All routine programmatic data are part of the clinical record and as such will not be destroyed.

Data Analysis

Objective 1: Statistical analysis plan for Objective 1. We propose a generalized linear mixed effects model, with random effect for clinic.[88] A simple model for $E(Y_{ij})$, the probability of ART initiation in the i th clinic at the j th time-point is given by:

$$\text{logit } E(Y_{ij}) = \beta_1 + \beta_2 \text{Group}_{ij} + b_i + e_{ij}$$

where b_i is a random effect for clinic i which accounts for clustering of patients within clinics, due perhaps to similarities in health-seeking behavior and/or access to care. β_1 is a fixed effect

corresponding to time j , $Group_{ij}$ is an indicator of intervention, and β_2 is the treatment effect (difference in log odds of ART receipt). We test the hypothesis, $H_0: \beta_2 = 0$. The mixed effects model will be extended to allow for covariate adjustment, such as: age, education, and distance from clinic. Separate models will be used to assess each outcome in each population (men, women, infants). For example, ART initiation among pregnant women ($n=1,080$) and then ART initiation among male partners ($n=1,080$). All adult patient models will include depression scale scores as covariates in attempts to control for potential presence of depression symptoms among participant groups. Female-specific models allow for inclusion of covariates unique to pregnant women, such as prior ANC, parity, etc. We also expect the intervention odds ratio to differ between women and their male partners. For infant HIV infection, sensitivity analyses will be conducted to investigate the effect of no EID test result on HIV infection; infants of mothers who did not initiate ART or were not retained in care at delivery will be assigned probabilities of infection (with definitions based on latest research). Then, infant HIV status will be multiply imputed using the Bernoulli distribution and estimates from the multiple regressions will be combined with multiple imputation techniques. An intent-to-treat approach will be employed for all analyses.

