Results from this study will be collected into a report, and will be shared with MISAU and the DPS. The results will also be disseminated to government officials and physicians working in these communities. If results are deemed by the authors to be potentially of interest to a wider scientific audience, we would plan on sharing these data in manuscript form, after obtaining appropriate clearances.

14. Budget

Description	TOTAL USD	MZM	Study Details	
Human Resources	60,000	4,200,000	Price per unit/person	Number of people/units
Project Officer (TBD)	30,000	2,100,000	30,000	1
Study Assistants	30,000	2,100,000	1,250	24
TRAVEL & TRANSPORT	14,670	1,026,900		
maintenance for car/gas (per day 44USD)	6,750	472,500	\$45	150
cell support for study assistants	2,880	201,600	10	24
basic nokia phone for each study assistant	960	67,200	40	24
bicycle repair kit	720	50,400	30	24
bicycles for peer supporters	3,360	235,200	140	24
TRAINING/PROJECT ACTIVITIES	5,980	418,600		
Training for Peer supporters				
per diem (food)	2,880	201,600	15	96
Venue hire	1,100	77,000	50	12
Training Materials	2,000	140,000	2,000	1
OTHER	2,500	175,000		
Laptop and accessories for Project Officer plus internet via movital	2,000	140,000	140,000	1
Photocopies of consent forms and questionnaire	500	35,000	0.25	
Total of all costs	83,150	5,820,500		
Contingency 10%	8,315	582050		
TOTAL	91,465	6,402,550		

15. Timeline

	Year 1	Year 2	Year 3	Year 4	Year 5
Version 2					

Study Activities	1	2	1	2	1	2	1	2	1	2
Staff and counselor hiring and (re)-training										
Enrollment of pregnant women & partners										
3, 6 , 12, and 18 month follow up										
Survey collection										
Fidelity assessments										
CEPAC model expansions										
Last study participant visits										
Data collection & management										
Data analysis										
CEPAC model inputs from trial data										
Model-based cost-effectiveness analyses										
Manuscript preparation										

Timeline of Study Activities

16. Bibliography

1. INSIDA: **National Survey on Prevalence, Behavioral Risks and Information about HIV and AIDS (2009 INSIDA)**. In. Maputo, Mozambique: Instituto Nacional de Saúde (INS), Ministry of Health (MISAU), & Instituto Nacional de Estatística (INE); 2009.
2. Ministerio da Saude (MISAU), Instituto Nacional de Estatística (INE), ICF International (ICFI): **Moçambique Inquérito Demográfico e de Saúde 2011**. In. Calverton, Maryland, USA: MISAU, INE e ICFI; 2013.

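### Clinics are randomised within 12 matched pairs, but the outcome models carry only a clinic random effect, with no pair term and no reference distribution suited to 24 clinics

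*Combined protocol and SAP*

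**What the plan says.** Section 6 (Design and Study Questions) describes a matched-pair cluster trial. On the matching it says "We will match clinics on ART uptake rates, retention in care among patients on treatment, patient volume, HIV prevalence in ANC", and facility level is the fifth variable. The investigators will "then randomize clinics in each matched pair to intervention and SOC arms", 12 clinics per arm.

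Section 10, Data Analysis, Objective 1: "We propose a generalized linear mixed effects model, with random effect for clinic". The displayed logistic model has an intervention coefficient (beta_2) and a clinic effect b_i, and the null hypothesis is beta_2 = 0. No statistic, reference distribution, degrees of freedom or small-sample correction is given. On covariates: "The mixed effects model will be extended to allow for covariate adjustment, such as: age, education, and distance from clinic". Depression scores and, for women, items such as parity are also mentioned. Neither the pair nor any matching variable is named.

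Objective 2 reuses this model with a linear outcome, and its structural equation model allows for clustering by clinic only. Section 8b has each psychosocial scale measured at baseline and by 6 months, but section 10 names the baseline score only for an interaction analysis.

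Section 9 holds "Table 2: Study Sites by intervention Status". Its rows run from 1 to 12, but nothing says that a row is a matched pair.

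**The concern.** The pairs are how the clinics were randomised, and they are built on variables close to the outcomes, such as ART uptake and retention. If matching works, the two clinics of a pair resemble each other, and the variance of the arm difference is smaller than a model with independent clinic effects assumes. The unpaired standard error is then too large. If matching does not work, only 24 randomised units remain, and a normal reference distribution makes the standard error look better known than it is.

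The two errors pull in opposite directions, so the plan does not fix the level of its own tests. That level may also differ between outcomes, because matching may predict retention better than it predicts viral suppression, infant outcomes or psychosocial scales. Section 10 makes no multiplicity adjustment, so the nominal level of each test is its only numerical control of false positives. The Objective 2 p-values also decide, at p<0.20, which mediators enter the structural equation model.

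**Working it through.** **Inputs from the documents.** 24 clinics in 12 pairs (section 6); 45 couples per clinic, alpha 0.05, and effects of 55% vs 71.5%, 31% vs 48% and 80% vs 90% (section 7d). Section 7e gives 40 couples per clinic, used here as a sensitivity case.

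**Assumed, because the documents are silent.** ICC 0.02 to 0.10; within-pair correlation rho of 0, 0.3, 0.5 or 0.7, meaning the share of between-clinic variance common to a pair; two-sided tests.

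**1. The plan's own power figure.** Section 7d claims over 80% power for 55% vs 71.5% but gives no ICC, so the figure cannot be reproduced exactly. With 540 women per arm and design effect 1 + 44 × ICC, ICC 0.05 gives 1 + 2.2 = 3.2, an effective 540/3.2 = 168.75 per arm and 88.5% power. At ICC 0.10 the design effect is 5.4, the effective number 100 and power 68.0%. The claim holds up to an ICC of about 0.07.

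**2. If matching explains nothing.** For clinic means, the unpaired statistic follows t with 22 df. Referred to the normal, its level is P(|t22| > 1.96) = 6.3%. Maximum likelihood divides by 24 where 22 is unbiased, so the effective cut-off is 1.96 × √(22/24) = 1.877 and the level is 7.4%. In fitted logistic models at a 55% rate, with ICC from 0.02 to 0.10, Wald z gave 6.6 to 8.0%, the likelihood-ratio test 5.7 to 6.2%, and t on 22 df 5.3 to 5.9%.

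**3. If matching works.** With known variances, the unpaired SE divided by the true SD is √{[ICC + (1−ICC)/45] / [ICC(1−rho) + (1−ICC)/45]}. At ICC 0.05, (1−ICC)/45 = 0.0211:
- rho 0.3: √(0.0711/0.0561) = 1.13
- rho 0.5: √(0.0711/0.0461) = 1.24
- rho 0.7: √(0.0711/0.0361) = 1.40

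**4. Level of Wald z with ML variance.** Random-intercept logistic model, 31% rate, 45 per clinic, 10,000 simulated trials per cell:

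| ICC | rho 0 | rho 0.3 | rho 0.5 | rho 0.7 |
|---|---|---|---|---|
| 0.02 | 7.2% | 5.3% | 4.0% | 2.8% |
| 0.05 | 7.5% | 4.4% | 3.0% | 1.7% |
| 0.10 | 7.0% | 4.5% | 2.1% | 1.0% |

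At ICC 0.05, an 80% rate gives 7.3 / 4.3 / 3.2 / 1.6%, and 40 couples per clinic gives 7.2 / 4.8 / 3.1 / 1.8%.

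**5. Alternatives.** In simulated clinic means over the same ICC range, unpaired t on 22 df runs at about 5% at rho 0 but falls to 0.5 to 1.8% at rho 0.7; paired t on 11 df stays at 5% throughout. A logistic model with random pair and clinic effects (31%, ICC 0.05) ran at 7.0 to 9.8% on z and 4.3 to 6.5% on t with 11 df. Permutation of within-pair differences in clinic log odds ran at 4.8 to 5.4%.

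**6. Power at ICC 0.05, pair model on t11 against unpaired z.**

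| Effect | rho 0 | rho 0.3 | rho 0.5 | rho 0.7 |
|---|---|---|---|---|
| 31% vs 48% | 88.0 vs 90.0 | 92.0 vs 91.4 | 95.9 vs 93.2 | 98.3 vs 94.7 |
| 55% vs 71.5% | 89.4 vs 91.1 | 93.6 vs 93.5 | 96.5 vs 93.9 | 99.0 vs 96.0 |
| 80% vs 90% | 78.6 vs 81.8 | 84.8 vs 84.3 | 89.6 vs 87.4 | 94.2 vs 88.9 |

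The differences run from about −3 to +5 points. Neither column is exactly at 5%: at rho 0 the z test runs at about 7% and the pair model at about 6%.

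**7. Baseline score, Objective 2.** Let r be the correlation between baseline and 6 months (assumed 0.3, 0.5, 0.7). If baseline explains only within-clinic variation, the SE ratio is √{[ICC + (1−ICC)(1−r²)/45] / [ICC + (1−ICC)/45]}, a reduction of 1, 4 or 8% at ICC 0.05. If r is the same at both levels it is √(1−r²), a reduction of 5, 13 or 29%.

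**The case against.** The strongest reply is that the plan never chose Wald z. With a likelihood-ratio test or t on 22 df, the excess at rho 0 shrinks to about 1 point or less. That stands: the 7% comes from the normal reference and the ML variance, not from ignoring pairs. It does not answer the point, because the plan leaves the choice open and t on 22 df stays conservative when matching works.

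Second, section 10 calls its model simple and keeps its covariate list open, so a pair term is permitted. That also stands: the term is unspecified, not excluded. A reader might infer that the investigators decided to break the matching, but the documents do not say so. An open list nevertheless leaves interval widths and p-values to a choice that could be made after outcomes are seen.

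Third, near rho 0.3 the unpaired z test is close to nominal, and the logistic pair model on t11 (5.7 to 6.0% there) is no closer. This is fair, and is the reason for keeping a permutation check.

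A reader might also infer that ignoring the pairs inflates false positives, or that the trial's error rate is 7%. Neither follows. When matching works the error is conservative, and no single rate can be attached to a test whose statistic, ICC and pair correlation are not given.

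**Conclusion.** The point stands as an improvement the SAP should make, not as a flaw that invalidates the trial. The randomisation uses 12 pairs; the specified models do not, and no reference distribution is fixed for 24 clinics. Under the stated assumptions (ICC 0.02 to 0.10, 45 per clinic), an unpaired Wald z test with ML variance could have a true level anywhere from about 7% to about 1%, depending on matching quality, which the documents do not report. The practical cost of good matching left unused is intervals that are too wide; the effect on power is a few points.

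The Objective 2 baseline-score question is minor. The standard error is valid without adjustment, and only precision is at stake, by an amount that depends on an assumed correlation.

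**What to change.** In section 10, Objective 1:
- List the 12 matched pairs, or state that the rows of the site table are the pairs if that is so.
- Index participants within clinic within pair.
- Make one analysis primary: the mixed model with a pair effect beside the clinic effect, and beta_2 tested on t with 11 degrees of freedom, not on z.
- Prespecify, as a sensitivity check, a within-pair permutation test over the 2^12 = 4,096 allocations, and name its statistic, for example the mean within-pair difference in clinic log odds.

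In Objective 2, use the same pair and clinic terms. Include each scale's baseline score as a main-effect covariate in the model that supplies beta_2, separate from the interaction analysis.

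**Cost.** SAP wording only; no new data or sites. The price is degrees of freedom. If matching explains nothing, a strict paired test on 11 df loses about 4 points of power to an unpaired t on 22 df, both at 5%. Using clinic summaries at ICC 0.05, the figures are 81.6% vs 85.2% for 31% vs 48%, and 71.2% vs 75.5% for 80% vs 90%. Power for 80% vs 90% is then below 80%; the pair model on t11 gives 78.6%. That model may run slightly above 5% (4.3 to 6.5% in simulation), which is why the permutation check is kept. The check itself has less power: for 80% vs 90% it gives 71.6% at rho 0 and 79.3% at rho 0.3. The baseline-score change is free.

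### The outcome models pre-specify none of the clinic characteristics used for matching, so precision is given up and chance clinic differences left after matching stay in the estimate

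*Combined protocol and SAP*

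**What the plan says.** Section 6 (Design and Study Questions) sets up a matched-pair cluster trial: "We will match clinics on ART uptake rates, retention in care among patients on treatment, patient volume, HIV prevalence in ANC, and level of facility", the last split into secondary and primary. It will "then randomize clinics in each matched pair to intervention and SOC arms", 12 clinics per arm.

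Section 10 (Data Analysis, Objective 1) states: "We propose a generalized linear mixed effects model, with random effect for clinic". The displayed model has a time-related fixed effect, an intervention indicator and a clinic intercept. On covariates: "The mixed effects model will be extended to allow for covariate adjustment, such as: age, education, and distance from clinic". Depression scores are added for all adults, with prior ANC and parity as examples for women. Objective 2 reuses the structure and describes its covariates as individual-level. No model contains a matching variable or a pair term.

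Section 9 lists the sites by arm under "Table 2: Study Sites by intervention Status", with name labels such as CS I, CS II, CS III, PS and PSA.

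**The concern.** With 12 clinics against 12, variation between clinics is a large part of the standard error of the treatment effect. The trial holds pre-trial clinic values that it judged prognostic enough to match on, two of them close to trial outcomes, and then leaves them out of the analysis.

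The clinic random intercept allows for between-clinic variation in the standard error, but does not correct a difference in this one allocation. Person-level covariates help only as far as their clinic averages differ and predict outcome. At stake are wider intervals than necessary and an estimate that carries whatever clinic differences the matching left. Because the covariate list is open-ended, a clinic covariate could still be added, but only by a choice that is not fixed in advance.

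**Working it through.** **Inputs.** From section 7d: 24 clinics, 45 couples per clinic, ART initiation 55% v 71.5%, α = 0.05 (two-sided assumed). The sampling paragraph (7e) gives 40 couples per clinic; this changes little below. Assumed, because the documents do not give them: the ICC, the clinic-level correlation *r* between baseline value and trial outcome, and the correlation ρ of baseline values within matched pairs.

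**1. The plan's power figure.** The plan states: "With 24 clusters and 45 couples per cluster, we have over 80% power to detect a 30% increase". Without clustering, 540 v 540 gives 99.99%. With clustering, power exceeds 80% only if the ICC is at most about 0.061 (cluster-level t, 22 df) or 0.070 (normal approximation). No ICC is stated, so the figure is compatible with the inputs but cannot be reproduced.

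**2. Share of variance between clinics.** In units of p(1−p), a clinic mean has variance ICC + (1−ICC)/45. At ICC 0.05 this is 0.0500 + 0.0211 = 0.0711, of which 0.0500/0.0711 = 70% is between clinics.

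**3. Proportional cut in the variance of the effect from adjustment.** Unadjusted, with matching: ICC(1 − ρr²) + (1−ICC)/45. Adjusted: ICC(1 − r²) + (1−ICC)/45. Hence

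cut = ICC·r²(1−ρ) / [ICC(1 − ρr²) + (1−ICC)/45].

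Example at ICC 0.05, r = 0.5, ρ = 0.5: 0.05 × 0.25 × 0.5 = 0.00625; the denominator is 0.05 × 0.875 + 0.0211 = 0.0649; the cut is 9.6%.

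| ICC | r | ρ = 0 | ρ = 0.5 | ρ = 0.8 |
|---|---|---|---|---|
| 0.02 | 0.5 / 0.7 | 12.0% / 23.5% | 6.4% / 13.3% | 2.6% / 5.8% |
| 0.05 | 0.3 | 6.3% | 3.3% | 1.3% |
| 0.05 | 0.5 / 0.7 | 17.6% / 34.5% | 9.6% / 20.8% | 4.1% / 9.5% |
| 0.10 | 0.5 / 0.7 | 20.8% / 40.8% | 11.6% / 25.7% | 5.0% / 12.1% |

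With 40 per clinic, ICC 0.05 and ρ = 0, the cuts are 16.9% and 33.2%.

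**4. Power for initiation, matching ignored, three clinic covariates charged (19 df).** SE = √[2 × 0.6325 × 0.3675 × (ICC(1−R²) + (1−ICC)/45)/12], with R² = r².

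| ICC | No covariate | R² = 0.25 | R² = 0.50 |
|---|---|---|---|
| 0.02 | 97.5% | 98.5% | 99.4% |
| 0.05 | 85.2% | 90.7% | 95.9% |
| 0.10 | 63.8% | 73.3% | 85.2% |

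If the covariates explain nothing, ICC 0.05 gives 84.6% instead of 85.2%.

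**5. Simulation with matching (ρ = 0.5, one clinic covariate, ICC 0.05).** Power rises from 90.6% to 93.4% (R² 0.25) or 96.7% (R² 0.50). The SD of the estimated log-odds ratio falls from 0.207 to 0.202 and from 0.201 to 0.185, which are variance cuts of 1 − (0.202/0.207)² = 4.8% and 1 − (0.185/0.201)² = 15.3%. These are below the formula values (9.6% at R² 0.25; 21.3% at R² 0.50), because the formula takes the covariate's coefficient as known. Average estimates were close to the true 0.72 with and without the covariate. With no true effect, across the matched settings (ρ 0.5 to 0.8), the model ignoring pair and covariate rejected 2.3% to 4.6% of the time; the adjusted model rejected about 5%.

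**6. Site labels.** CS I or CS II: 1 intervention v 3 control. CS III: 6 v 4. PS or PSA: 3 v 3. CS without a level: 2 v 2. If rows are pairs, which is not stated, labels agree in rows 1, 7 and 11 only.

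**The case against.** The strongest reply is that the clinics were already matched on these variables, so much of the gain has been taken by design. This stands: the 18–35% applies only if matching achieved nothing, and the cut falls to about 4–10% when pairs are close.

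Second, the retention used for matching is among patients on treatment, whereas section 7d counts people who never start ART as retention failures and analyses women and men separately. It is therefore a proxy, and a correlation of 0.5 to 0.7 is unsupported. This also stands, and it shapes the fix.

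Third, the Objective 1 list is only illustrative, and distance, education or prior ANC may differ between clinics. It would be wrong to say that person-level covariates explain no between-clinic variation. They do not, however, replace the clinic's own past rate, and permission to add a covariate is not pre-specification.

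A reader might infer from the site table that matching failed, or that the estimate is biased. The documents support neither. The name labels are not mapped to the secondary/primary variable, rows are not said to be pairs, and clinic-level uptake and retention are not shown. Randomisation keeps the unadjusted estimate unbiased.

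**Conclusion.** The gap is real: no Objective 1 or 2 model uses a matching variable. It is a matter of efficiency and of chance imbalance in one allocation; the analysis remains valid without the change. The likely size is a modest to moderate variance reduction: at ICC 0.05 and r = 0.5–0.7, about 10–21% with moderately similar pairs and 4–10% with close pairs, somewhat less once the coefficient is estimated from 24 clinics. At ICC 0.02 power is already about 97% and only 1–2 points are gained; at r = 0.3 the gain is roughly cancelled by its cost. The ICC, r and ρ are all assumptions. Because the stated power holds only up to an ICC of about 0.06–0.07, the change should be made: precision matters most where the plan has least margin.

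**What to change.** State in section 10 that each Objective 1 model includes two clinic-level covariates from the matching dataset:

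1. pre-trial ART uptake for initiation, and pre-trial uptake × retention for retention and downstream outcomes, mirroring the section 7d calculation (0.55 × 0.56 = 0.31);
2. facility level in the two categories used for matching.

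Report the model without them as a sensitivity analysis. First confirm that the values are complete for all 24 clinics: the documents do not say so, and the title of the cited matching reference refers to missing data.

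The cost is one sentence and two of about 22 between-clinic degrees of freedom. Counting degrees of freedom alone, that is under 1 point of power if the covariates explain nothing. Chance association with arm can add to this: with wholly unmatched, useless covariates the expected variance factor is 21/19 = 1.105, so at ICC 0.05 the SE goes from 5.25 to 5.52 points and power from 85.2% to about 81%. Close matching removes most of that extra cost. Two covariates should be the limit; entering the separate site labels as a factor would cost far more.
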